### **10.1.4 Confidentiality**

All information generated in this trial will be considered confidential and will not be disclosed to anyone not directly concerned with the trial without the sponsor's prior written permission. Subject confidentiality requirements of the region(s) where the trial is conducted will be met. However, authorized regulatory officials and sponsor personnel

(or their representatives or development partners) may be allowed full access to inspect and copy the records, consistent with local requirements. All IMPs, subject bodily fluids, and/or other materials collected shall be used solely in accordance with this protocol, unless otherwise agreed to in writing by the sponsor.

Subjects will be identified only by unique subject ID in eCRF. If further subject identification is required, subjects' full names may be made known to a regulatory agency or other authorized officials if necessary, subject to local regulations.

#### **10.1.5 Reporting of Safety Issues and Serious Breaches of the Protocol or ICH GCP**

In the event of any prohibition or restriction imposed (ie, clinical hold) by an applicable Competent Authority, or if the investigator is aware of any new information which might influence the evaluation of the benefits and risks of the investigational product, the sponsor should be informed immediately.

In addition, the investigator will inform the sponsor immediately of any urgent safety measures taken by the investigator to protect the trial subjects against any immediate hazard, and of any serious breaches of this protocol or of ICH GCP, defined as a breach that will likely affect the safety or physical or mental integrity of subjects or the scientific value of the trial, that comes to the attention of the investigator.

#### **10.1.6 Quality Control and Quality Assurance**

##### **10.1.6.1 Monitoring**

The sponsor has ethical, legal, and scientific obligations to follow this trial in accordance with established research principles, the ICH GCP: Consolidated Guideline (E6), and applicable regulatory requirements and local laws. As part of a concerted effort to fulfill these obligations (maintain current personal knowledge of the progress of the trial), the sponsor's monitors will visit the site during the trial, as well as communicate frequently via telephone, e-mail, and written communications. In addition, all investigators and trial site personnel will undergo initial and ongoing training for this particular trial, and this training will be clearly documented.

##### **10.1.6.2 Auditing**

The sponsor's Quality Assurance Unit (or representative) may conduct trial site audits. Audits will include, but are not limited to, IMP supply, presence of required documents, the informed consent process, and a review of the eCRF with source documents, as applicable. The investigator agrees to participate with audits. It is important that the

investigator(s) and their relevant personnel are available during the monitoring visits and possible audits or inspections and that sufficient time is devoted to the process.

Regulatory authorities may inspect the investigator site during or after the trial. The investigator will cooperate with such inspections and will contact the sponsor immediately if such an inspection occurs.

### **10.1.7 Protocol Deviations**

In the event of a significant deviation from the protocol due to an emergency, accident, or mistake (eg, violation of informed consent process, IMP dispensing or subject dosing error, treatment assignment error, subject enrolled in violation of eligibility criteria or concomitant medication criteria, fraud or misconduct, increased health risk to the subject, or confounded interpretation of primary trial assessments), or except where necessary to eliminate an immediate hazard to trial subjects, the investigator or designee will contact the sponsor or designee (and IRB/IEC, as required) at the earliest possible time by telephone or via e-mail. If needed, the investigator and sponsor (or designee) will come as quickly as possible to a joint decision regarding the subject's continuation in the trial. This decision will be documented by the investigator and the sponsor (or designee) and reviewed by the site monitor.

Any major protocol deviation will be recorded in the eCRF along with the start date and details of the deviation.

### **10.1.8 Records Management**

#### **10.1.8.1 Source Documents**

Source documents are defined as the results of original observations and activities of a clinical investigation. Source documents will include but are not limited to medical records, electronic data, screening logs, dialysis records or flow sheets, and recorded data from automated instruments. All source documents pertaining to this trial will be maintained by the investigators and made available for direct inspection by authorized persons.

Investigator(s)/institution(s) will permit trial-related monitoring, audits, IRB/IEC review, and regulatory inspection(s) by providing direct access to source data/documents by authorized persons as defined in the ICF. In all cases, subject confidentiality must be maintained in accordance with local regulatory requirements.

### **10.1.8.2 Data Collection**

During each subject's visit to the site, an investigator or their designee participating in the trial will record information to document all significant observations. At a minimum, these notes will contain:

- Documentation of the informed consent process, including any revised consents;
- Documentation of the investigator's decision to enroll the subject into the trial, the review of all inclusion/exclusion criteria prior to IMP administration, and confirmation of the subject's actual participation in the trial;
- The date of the visit and the corresponding Visit or Day in the trial schedule;
- General subject status remarks, including any *significant* medical findings. The severity, frequency, duration, action taken, and outcome of any AEs and the investigator's assessment of relationship to IMP must also be recorded;
- Any changes in concomitant medications or dosages;
- A general reference to the procedures completed;
- The signature (or initials) and date of the investigator (or designee) who made an entry in the medical record.

In addition, any contact with the subject via telephone or other means that provides significant clinical information will also be documented in the progress notes as described above.

Information from medical records and other source documents will be entered by investigative site personnel onto eCRFs in the sponsor's EDC system that is 21 Code of Federal Regulations (CFR) Part 11 compliant. Changes to the data will be captured by an automatic audit trail in the EDC system.

Electronic data not entered on eCRF, such as data received from central laboratories will be reconciled using key data fields by the sponsor or the CRO with the eCRF data to ensure consistency.

### **10.1.8.3 File Management at the Trial Site**

The investigator will ensure that the trial site file is maintained in accordance with Section 8 of the ICH GCP: Consolidated Guideline (E6) and as required by applicable local regulations. The investigator/institution will take measures to prevent accidental or premature destruction of these documents.

#### **10.1.8.4 Records Retention at the Trial Site**

Regulatory requirements for the archival of records for this trial necessitate that participating investigators maintain detailed clinical data for the longest of the following 3 periods:

- A period of at least 2 years after the date on which approval to market the drug is obtained (or if IMP development is discontinued, the date regulatory authorities were notified of discontinuation); OR
- A period of at least 3 years after the sponsor notifies the investigator that the final report has been filed with regulatory authorities.
- Longer, region-specific storage requirements, if applicable.

The investigator must not dispose of any records relevant to this trial without either (1) written permission from the sponsor or (2) provision of an opportunity for sponsor to collect such records. The investigator will be responsible to maintain adequate and accurate electronic or hard copy source documents of all observations and data generated during this trial including any data clarification forms received from the sponsor. Such documentation is subject to inspection by the sponsor and relevant regulatory authorities. If the investigator withdraws from the trial (eg, due to relocation or retirement), all trial-related records should be transferred to a mutually agreed-upon designee within a sponsor-specified timeframe. Notice of such transfer will be given to the sponsor in writing.

#### **10.1.8.5 Publication of Trial Results**

No publication or disclosure of trial results will be permitted, except under the terms and conditions of a separate, written agreement between the sponsor (Otsuka Pharmaceutical Development & Commercialization, Inc. [OPDC] in collaboration with Akebia) and the investigator and/or the investigator's institution. The sponsor and Akebia must have the opportunity to review and approve all proposed abstracts, manuscripts, or presentations regarding this trial prior to submission for publication/presentation. Any information identified by the sponsor or Akebia as confidential must be deleted prior to submission.

For all publications relating to the trial, the institution will comply with recognized ethical standards concerning publications and authorship, including: Section II - "Ethical Considerations in the Conduct and Reporting of Research" of the Uniform Requirements for Manuscripts Submitted to Biomedical Journals, <http://www.icmje.org/index.html#authorship>, established by the International Committee of Medical Journal Editors (ICMJE).

#### **10.1.8.5.1 Publication Authorship Requirements**

Authorship for any Otsuka- or Akebia-sponsored publications resulting from the conduct of this trial will be based on ICMJE authorship criteria

(<http://www.icmje.org/recommendations>). According to ICMJE guidelines, one may be considered an author only if the following criteria are met:

- 1) Substantial contributions to the conception or design of the work; or the acquisition, analysis, or interpretation of data for the work; AND
- 2) Drafting the work or revising it critically for important intellectual content; AND
- 3) Final approval of the version to be published; AND
- 4) Agreement to be accountable for all aspects of the work in ensuring that questions related to the accuracy or integrity of any part of the work are appropriately investigated and resolved.

All authors must meet the above criteria, and all who qualify for authorship based on the above criteria should be listed as authors.

Investigators or other trial subjects who do not qualify for authorship may be acknowledged in publications resulting from the trial. By agreeing to participate in the trial, investigators or other trial subjects consent to such acknowledgement in any publications resulting from its conduct.

## 10.2 Appendix 2: Clinical Laboratory Tests

The investigator and the sponsor will maintain a copy of the laboratory accreditation and the reference ranges for the central laboratory used for clinical laboratory evaluations. Additionally, other accreditation(s) will be collected as required.

The tests detailed in [Table 10.2-1](#) will be performed.

Table 10.2-1 Clinical Laboratory Assessments		
Complete Blood Count	Iron Indices	Serum Chemistry
Hb	Ferritin	Sodium
Hematocrit	Iron	Potassium
RBC	TIBC	Bicarbonate
MCV	TSAT	Chloride
MCH		Calcium
MCHC		Magnesium
Platelets	Lipid Profile	Phosphorus
RDW	Total Cholesterol	Glucose
WBC	LDL	Creatinine
Differential WBC	HDL	BUN
Neutrophils	Triglycerides	CPK
Lymphocytes		Uric Acid
Monocytes	Liver Function Tests	Albumin
Eosinophils	Total bilirubin	Total Protein
Basophils	ALP	
Hematology panel without differential	ALT/SGPT	
Hb	AST/SGOT	
Hematocrit	LDH	
RBC		
MCH		
MCHC		
RDW		
RBC morphology and MCV		
Platelets		
WBC		
Additional Laboratory Tests		
β-HCG		
Reticulocyte Count a		
Folate		
Vitamin B 12		
CRP		
Erythropoietin		
INR b		
PT b		

β-HCG = beta human chorionic gonadotropin; ALP = alkaline phosphatase; ALT = alanine aminotransferase; AST = aspartate aminotransferase; BUN = blood urea nitrogen; CPK = creatine phosphokinase; CRP = C-reactive protein; Hb = hemoglobin; HDL = high density lipoprotein; INR = international normalized ratio; LDH = lactate dehydrogenase; LDL = low density lipoprotein; MCH = mean corpuscular hemoglobin; MCHC = mean corpuscular hemoglobin concentration; MCV

= mean corpuscular volume; PT = prothrombin time; RBC = red blood cell; RDW = red blood cell distribution; SGOT = serum glutamic-oxaloacetic transaminase; SGPT = serum glutamic-pyruvic transaminase; TIBC = total iron-binding capacity; TSAT = transferrin saturation; WBC = white blood cell.

aAn automated reticulocyte count should include both absolute and percent.

bINR and PT to be collected at the discretion of the investigator and sent to the central laboratory for analysis only if ALT or AST > 3x ULN to evaluate stopping criteria.

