### 7.3.2 Treatment Discontinuation

After treatment assignment, a subject may stop treatment permanently for a variety of reasons. Treatment discontinuations may be initiated by a subject who is not satisfied with treatment or may become medically necessary due to AEs, required treatment with a disallowed medication or therapy, or other issues, as determined by the investigator.

However, each investigator must comprehensively review the circumstances and offer the subject options for continued treatment to the degree possible. If, after discussion with the investigator about possible mitigations for AEs, etc., the subject still chooses to discontinue IMP, the subject will permanently discontinue IMP and will complete the ET Visit assessments and will complete the Safety Follow-Up Visit, 4 weeks after last dose of IMP and the subject will not be allowed to re-start the IMP.

Trial medication is to be permanently discontinued if ESA rescue (other than darbepoetin alfa in comparator arm, any ESA in vadadustat arm) is not in the setting of acute bleeding (ie, gastrointestinal bleed, surgery, excess bleeding) and one of the following:

- The first cycle of ESA rescue lasts >30 days or
- Subject requires a second cycle of ESA for rescue (that must be related to anemia) at any time.

Trial medication must be permanently discontinued if a subject meets one of the criteria in [Table 7.3.2-1](#).

Table 7.3.2-1 Trial Medication Stopping Rules	
ALT or AST > 3x ULN and total bilirubin > 2x ULN	Permanently Discontinue Treatment
ALT or AST > 3x ULN and INR > 1.5	Permanently Discontinue Treatment
ALT or AST > 8x ULN	Permanently Discontinue Treatment
ALT or AST remains > 5x ULN over 2 weeks a	Permanently Discontinue Treatment
ALT or AST > 3x ULN with symptoms including eg, fatigue, nausea, vomiting, right upper quadrant pain, fever, rash or eosinophilia	Permanently Discontinue Treatment

INR: international normalized ratio; ULN: upper limit of normal

aRe-challenge generally should be avoided with ALT or AST > 5x ULN unless there are no other good therapeutic options.

See [Section 8.8](#) for reporting requirements related to a subject being permanently discontinued based on meeting the laboratory abnormalities list above in [Table 7.3.2-1](#).

For subjects who permanently discontinue IMP, the investigator will resume standard of care treatment, including ESAs and iron therapy, as deemed appropriate.

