### 8.7.1 Clinical Laboratory Assessments

Clinical laboratory samples will be collected at the time points described in the Schedule of Assessments ([Table 1.3-1](#)) to perform the clinical laboratory assessments described in [Section 10.2](#).

Samples for laboratory assays will be sent to a central laboratory for analysis. Detailed instructions for the collection, processing, and shipment of laboratory samples will be provided by the central laboratory. If blood is collected on a hemodialysis day, blood draws should be done prior to dialysis, if applicable. The investigator is responsible for reviewing laboratory results for clinical significance.

Blood samples will be collected for the laboratory evaluations listed in [Section 10.2](#) and will be conducted during the course of the trial. For details regarding the timing of these assessments refer to the Schedule of Assessments ([Table 1.3-1](#)).

- **Pregnancy Test:** A serum pregnancy test will be performed according to the Schedule of Assessments ([Table 1.3-1](#)) for females of childbearing potential. Additional serum or local urine (if possible) pregnancy tests may be conducted throughout the trial in sufficient number, as determined by the investigator or required by local regulations,

to establish the absence of pregnancy during the trial. These results must be available and must be negative before the subject takes the first dose of IMP.

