Table 10.2-1 (Clinical Laboratory Assessments)	Updated “Complete Blood Count,” “Iron Indices” and instructions for “INR and PT collection.” Also added “Hematology panel without differential.”
Section 11 (References)	The list of references was updated.

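### One mandatory liver stopping rule depends on an INR that the protocol leaves to the investigator's discretion

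*Protocol*

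**What the plan says.** Protocol Section 7.3.2 makes the liver stopping table binding: "Trial medication must be permanently discontinued if a subject meets one of the criteria in" Table 7.3.2-1. The second of its five rows is "ALT or AST > 3x ULN and INR > 1.5".

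Whether an INR is drawn is governed by footnote b of Table 10.2-1 (Section 10.2, Appendix 2): "INR and PT to be collected at the discretion of the investigator". The same footnote has the sample sent to the central laboratory "only if ALT or AST > 3x ULN to evaluate stopping criteria".

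Two general sentences point towards routine collection. Section 10.2 opens with "The tests detailed in" Table 10.2-1 and says they will be performed. Section 8.7.1 says "Blood samples will be collected for the laboratory evaluations listed in" Section 10.2. Section 8.7.1 also states: "Detailed instructions for the collection, processing, and shipment of laboratory samples will be provided by the central laboratory".

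For a new ALT or AST above 3 times the upper limit of normal (ULN) without bilirubin above 2 times ULN, Sections 8.8.1 and 8.8.2.1 require three things: interruption of IMP, a repeat of ALT, AST, ALP and total bilirubin within 48 to 72 hours, and no resumption until the abnormalities have resolved or are stable. Section 7.3.1 adds that the decision to restart is assessed with the Medical Monitor or CRO designee within 30 days.

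**The concern.** A rule that obliges a permanent stop should rest on data the protocol obliges the site to collect. Here the rule is mandatory and one of its two inputs is optional. The group for whom the INR row adds protection is also the group sent down the interrupt, repeat and possibly restart route, and no step on that route asks for an INR.

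What is at stake is re-exposure of a subject who, by the protocol's own criterion, should never restart. Section 2.4 lists hepatotoxicity as a confirmed important identified risk of vadadustat and reports drug-induced liver injury possibly or probably related to it, although all those subjects recovered without sequelae. This is a subject-safety point only. The SAP's potential liver injury summaries (Section 10.5.1) use ALT, AST and bilirubin, and no planned efficacy analysis uses INR.

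**Working it through.** The plan gives no figure to reproduce, so the check is first one of text against text.

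**Is each stopping row evaluable from required data?**

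| Table 7.3.2-1 row | Input beyond ALT/AST | Required by the protocol? |
|---|---|---|
| > 3x ULN with bilirubin > 2x ULN | Total bilirubin | Yes: liver panel and repeat panel |
| > 3x ULN with INR > 1.5 | INR | No: investigator's discretion |
| > 8x ULN | None | Yes |
| > 5x ULN over 2 weeks | None | Yes |
| > 3x ULN with symptoms | Symptoms | Yes: subjects are asked about adverse events at each visit |

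**Does any other text require the INR?**

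- Schedule of Assessments (Section 1.3), footnote j: the liver panel is bilirubin, ALP, ALT, AST and LDH. There is no INR.
- Sections 8.8.1 and 8.8.2.1: both statements of the repeat panel list the same four analytes, without INR.
- Restart conditions in Sections 7.3.1, 8.8.1 and 8.8.2.1: none mentions INR. Stable does not mean normal, so an asymptomatic subject steady at 4 times ULN could be restarted with INR unknown.
- The general sentences in Sections 8.7.1 and 10.2: these cover every test in the table, whereas footnote b is attached specifically to INR and PT. The specific note governs.
- The Amendment 1 change table records that the instructions for "INR and PT collection" were updated. The discretion is therefore read as a deliberate choice, not a slip.

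**Who falls in the gap?** Subjects with ALT or AST above 3 times ULN who meet none of the other four rows: bilirubin not above 2 times ULN, transaminases not above 8 times ULN, not above 5 times ULN over 2 weeks, and no symptoms.

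**How many?** The documents give no rates. The base is about 200 vadadustat subjects (100 QD plus 100 TIW, Section 5). All three rates below are assumptions.

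| Assumed rate | Low | Middle | High |
|---|---|---|---|
| a: in the gap | 1% | 2% | 4% |
| b: INR > 1.5 for any reason, given a | 2% | 5% | 20% |
| c: INR not drawn, given a and b | 25% | 50% | 75% |

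Missed stops = 200 × a × b × c.

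- Subjects in the gap: 200 × 0.01 = 2, 200 × 0.02 = 4, 200 × 0.04 = 8.
- Middle case: 200 × 0.02 × 0.05 × 0.50 = 0.10.
- Varying a alone: 0.05 to 0.20. Varying b alone: 0.04 to 0.40. Varying c alone: 0.05 to 0.15.
- All low: 200 × 0.01 × 0.02 × 0.25 = 0.01.
- All high: 200 × 0.04 × 0.20 × 0.75 = 1.2. This stacks three extremes and is not a realistic expectation.

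**The case against.** The strongest reply is that footnote b should be read whole and in context. It names the trigger and the purpose of the test. Section 7.3.2 puts a firm obligation on every stopping row, and Sections 7.3 and 8.8.2.1 refer the investigator back to Table 7.3.2-1 for ALT and AST abnormalities. Restart is discussed with the Medical Monitor, the event is reported as an SAE within 24 hours, and a hepatic expert panel exists. Subjects with chronic liver disease, or with ALT, AST or bilirubin above 1.5 times ULN, are excluded at screening. A careful investigator would probably draw the INR. These points make a missed stop unlikely, but none of them compels the test. The cross-references lead only to the stopping table, and neither the Medical Monitor nor the panel can review a value that was never obtained.

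A second reply is that INR is confounded by anticoagulants, for which the protocol has neither an exclusion nor an exception in the stopping row, so discretion is one way to handle it. That has some force. It also means the illustrative count includes raised INRs that are not hepatic, so it overstates the liver-safety benefit. But the confounding lies in the row as written. Making the test optional leaves the rule in place and applies it unevenly.

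Third, the symptom row is open-ended and includes fatigue and nausea. The protocol itself describes fatigue as a symptom of anemia and nausea as common in dialysis patients, so many affected subjects may already have to stop under that row. This stands, and it could make the gap smaller than the assumed 1% to 4%.

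Finally, the central laboratory's collection instructions were not available and may require the INR. If they do, the protocol should be brought into line with them.

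**Conclusion.** The concern holds. One of five permanent-discontinuation criteria cannot be evaluated from the data the protocol requires, and a site following the text can restart a subject who meets that criterion untested. The textual finding is firm for the documents as seen, subject to whatever the central laboratory's instructions add. The practical size is very small: 0.10 missed stops in the middle case and 0.04 to 0.4 when one rate is varied at a time, all on assumed rates and counting INR above 1.5 from any cause. It may be zero. The case for correction rests on a mandatory safety rule for a known drug risk being unenforceable, not on frequency. It should be fixed, and it does not threaten the trial's conclusions.

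**What to change.** 1. In Sections 8.8.1 and 8.8.2.1, add INR and PT to the 48 to 72 hour repeat panel for a new ALT or AST above 3 times ULN. State that IMP is not resumed until the INR has been checked against Table 7.3.2-1.
2. In footnote b of Table 10.2-1, remove the reference to investigator discretion, so that INR and PT are collected whenever ALT or AST exceeds 3 times ULN and only then.

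The stopping row and the pre-dialysis draw instruction need no change. The cost is two wording changes and one extra tube, at a draw already required, for about 2 to 8 vadadustat subjects under the assumed rates, or 300 × 0.01 = 3 to 300 × 0.04 = 12 if the darbepoetin arm had the same rate. The assay is already listed, and waiting for the result fits within the 30-day interruption limit. The one drawback is that some subjects on anticoagulants that raise INR may be found to meet the row as it already stands and would have to stop. Whether to write an exception for them is for the sponsor to decide.
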